The Week 24 end of study visit of the parent study (AV-101-002) also represents the baseline visit for the LTE study (AV-101-003). The following assessments will be conducted/collected during the baseline visit of the LTE and at selected time points specified in the Schedule of Assessments (Table 1). Additional procedures deemed necessary as part of standard of care may be performed at the discretion of the Investigator. All missed visits and any performed procedures that are not protocol-specified activities must be documented in the subject's medical record and the appropriate eCRF. General considerations for study visits include, but are not limited to the following:

- No protocol waivers or exemptions are allowed.
- Immediate safety concerns should be discussed with the CRO Medical Monitor immediately upon occurrence or awareness to determine if the subject should continue or discontinue study drug.
- Adherence to the study design requirements, including those specified in the Schedule of Assessments, is essential and required for study conduct (see Section 6.7.1 for COVID-19 considerations).
- The Investigator will obtain written informed consent before the end of study visit for study AV-101-002 and as specified in Section 9.1.3 (Informed Consent Process). Upon the subject's agreement, their primary health care provider should be informed about the subject's enrollment in the study.
- Order of Procedures:
 - Health-related QoL assessments should be performed prior to all other study procedures.
 - Vital signs should be collected prior to blood draws. Blood samples for NT-proBNP levels should be collected prior to the 6MWT.
 - All other study assessments should also be performed, according to the Schedule of Assessments (Table 1).
- **Unscheduled visits:** may occur at any time during the study with the assessments to be performed according to the Investigator's judgment. Unscheduled visits may also be necessary for study drug dispensing following temporary withdrawal as described in Sections 6.7 and 7.7.

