8.1 Introduction: Study Design and Analysis Overview

The LTE is a longitudinal study of the long-term safety and effectiveness of PAH patients treated with AV-101 at different dose levels until being transitioned to the optimal dose of AV-101 which is selected after the completion of the Phase 2b Part of Study AV-101-002 (referred to as the parent study). About 370 subjects (with a maximum of 462 subjects) are expected to start the LTE. LTE subjects may be grouped into the following treatment groups:

- **Group 1 – Optimal Dose Treatment:** Subjects treated with the optimal dose throughout the parent trial and throughout their LTE participation.
- **Group 2 – Non-Optimal Dose Active Treatment, then Optimal Dose Treatment:** Subjects treated with active doses not selected as the optimal dose, who eventually will be treated with the optimal dose when this dose is selected.
- **Group 3 – Placebo to Non-Optimal Dose, then Optimal Dose Treatment:** Subjects originally assigned to the placebo arm during the parent trial then re-randomized to the two non-optimal active groups. Later, they will receive the optimal dose when it is selected.
- **Group 4 – Placebo to Optimal Dose Treatment:** Subjects originally assigned to the placebo arm during the parent trial then either re-randomized or switched to optimal dose.

Further characteristics of these LTE treatment groups are described in [Section 8.3](#).

Among the comparisons to consider are:

- 1) LTE levels and trends among subjects always on the optimal dose Group 1 will be compared in order with those of:
 - Group 4: Placebo to optimal dose treatment
 - Group 3: Placebo to non-optimal dose, then optimal dose treatment
 - Group 2: Non-optimal dose active treatment, then optimal dose treatment
- 2) Levels and trends in LTE safety and effectiveness endpoints for subjects always on the optimal dose (Group 1) will be compared to levels and trends during the parent study among these same subjects. This will be done to document whether the effects of the previous optimal dose on subsequent measures of effectiveness and safety while still undergoing treatment persist, improve, plateau, or dip the longer the duration of the optimal treatment.
- 3) Trends in continuous LTE effectiveness endpoints will be assessed separately for continuous dose intensity and continuous relative dose intensity.

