8.4 Baseline and Demographics and Subject Study Disposition

With exception of the delayed-start analysis, for both the efficacy and safety analyses, baseline will be defined as the time prior to starting active treatment with AV-101 in either the LTE or the parent study. For Groups 1 and 2, since the subjects start receiving active treatment in the parent study, the baseline will be the values prior to first dose during the parent trial. For Groups 3 and 4, the subjects receive placebo in the parent trial and then receive active treatment in the LTE study, thus, the baseline will be the values prior to the first dose in LTE study.

Demographics and baseline data, medical and surgical history will be summarized using the screened analysis set. These demographics and baseline data will be presented by the LTE treatment groups as described in [Section 8.1](#).

Demographic and baseline data will be summarized using summary statistics of mean, standard deviation, median, lower quartile, upper quartile, min and max for continuous variables and number and percentage of subjects in each category.

Subject treatment status and study participation status will be reported for the safety analysis set. Subjects who completed all LTE assessments and early treatment discontinuation and withdrawal from the study including reasons for treatment or study discontinuation will be reported by LTE treatment groups.

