Unstructured covariance will be specified. If the fitted model does not converge with unstructured covariance, a simpler covariance will be specified. LSMeans by trial treatment groups and difference in mean change from baseline in NT-proBNP at each visit will be reported. At each post-baseline visit (with focus on Weeks 24, 48 and 72 after LTE entry) the difference in mean change from baseline in NT-proBNP between treatment groups and its 95% CI for the treatment term will be reported. The mean difference in change from LTE baseline between subjects always on the optimal dose will be compared in the following order: 1) always on placebo (Group 4); 2) placebo followed by an active treatment dose (Group 3); 3) always on the non-optimal dose (Group 2). Average treatment effectiveness before and after optimal dose treatment during the LTE will also be presented.

Trends in change from baseline (CFB) will initially be assessed graphically. To obtain a measure of trends using MMRM, visits as continuous variables, and visit by LTE treatment groups interactions will be entered into the model. The coefficient for continuous visit associated for each of the LTE treatment groups indicates the linear trend in change from baseline over visit. A non-linear trend in CFB will be tested by entering visit as quadratic or cubic spline of visit in the model.

3) Maintenance or improvement in WHO Functional Class throughout the LTE

At each post-LTE baseline visit, a subject's status with respect to remaining in or decreasing from the same WHO FC will be recorded. At each post-baseline visit, the proportion of subjects who remain or improve on their baseline WHO FC will be reported by treatment groups. A logistic regression model will be fitted where the response at each visit is whether the subject remains in or improves in WHO FC. The explanatory variables consist of LTE treatment groups, visit, LTE treatment groups by visit, IPA/HPA or non-IPA/HPA category, and continuous LTE baseline REVEAL Lite 2.0 score.

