A Cox model will be fitted to time to clinical worsening with terms for time-varying by treatment dose groups, continuous LTE baseline REVEAL Lite 2.0 score (among those randomized to placebo in Phase 3), continuous parent baseline REVEAL Lite 2.0 score, and IPAH/HPAH or Non-IPAH/HPAH category.

The hazard ratio and its 95% CI for the pairwise treatment dose groups will be reported for:

- Always on the optimal dose (Group 1) versus always on placebo (Group 4)
- Always on the optimal dose (Group 1) versus on placebo followed by an active dose (Group 3)
- Always on the optimal dose (Group 1) versus always on a non-optimal dose (Group 2)

Kaplan-Meier curves by parent trial treatment groups will be generated.

5) Achieving multicomponent clinical improvement will be analyzed as a binary as well as a time to event response throughout the LTE period

a) Binary response throughout LTE period: At each LTE visit, a subject response is set to 1 for achieving multicomponent clinical improvement if he meets all of the following three conditions:

- FC improvement or maintenance of FC II status
- NT-proBNP \geq 30% improvement or $<$ 300 pg/ml
- 6MWD \geq 30 meters improvement

Otherwise, the response value is 0.

A logistic regression model will be fitted to the binary response of achieving multicomponent clinical improvement at each visit. The explanatory variables will include LTE treatment groups categorical visit, LTE treatment groups by visit interaction, continuous LTE baseline REVEAL Lite 2.0 score, continuous parent baseline REVEAL Lite 2.0 score, and IPAH/HPAH or Non-IPAH/HPAH category. The subject's multicomponent clinical improvement status during the parent study may be considered as an explanatory variable. Subjects will be specified as clusters.

b) **Time to Event Response from start to end of the LTE:** Time to achieve multicomponent clinical improvement response is defined as the days since the first

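### The WHO FC and clinical-improvement logistic models adjust for REVEAL Lite 2 at LTE entry, which Groups 1 and 2 reach after 24 weeks on AV-101, so their odds ratios condition on a post-treatment variable

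*Combined protocol and SAP*

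**What the plan says.** Item 3 of Section 8.5.2 fits a logistic model, visit by visit within subject, to whether a subject stays in or improves on the baseline WHO FC. Apart from group and visit, its explanatory terms end with "LTE treatment groups by visit, IPA/HPA or non-IPA/HPA category, and continuous LTE baseline REVEAL Lite 2.0 score". The parent-baseline score is not in this model.

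Item 5a does the same for multicomponent clinical improvement, with "continuous LTE baseline REVEAL Lite 2.0 score, continuous parent baseline REVEAL Lite 2.0 score" both entered. It adds that the subject's "multicomponent clinical improvement status during the parent study may be considered as an explanatory variable".

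Sections 6 and 6.1 make the Week 24 visit of AV-101-002 the baseline visit of the LTE. Section 8.1 defines Group 1 as "Subjects treated with the optimal dose throughout the parent trial and throughout their LTE participation", and Group 2 as subjects on the other active doses. Groups 3 and 4 took placebo in the parent trial.

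Section 8.4 sets baseline before the first AV-101 dose for all efficacy and safety analyses except the delayed-start analysis. For Groups 1 and 2, "the baseline will be the values prior to first dose during the parent trial"; for Groups 3 and 4 it is the value before the first LTE dose.

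Other models in Section 8.5.2 treat REVEAL differently. The MMRM in item 2 uses the parent-trial score. The clinical-worsening Cox model in item 4 uses the parent score and restricts the LTE-entry score to subjects randomized to placebo in Phase 3.

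**The concern.** One covariate carries two meanings across the groups being compared. In Groups 3 and 4 the LTE-entry score is a pre-drug characteristic. In Groups 1 and 2 it is partly a result of 24 weeks on drug. Table 3 builds it from WHO FC, 6MWD and NT-proBNP (plus renal function, blood pressure and heart rate), and the first three are the components of the clinical-improvement response, down to the shared 300 pg/mL cut-off. WHO FC is itself the item 3 response.

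Under Section 8.4 the response in Groups 1 and 2 counts change since before the first parent dose. The model would then hold fixed a variable through which part of that change acts. A Group 1 subject who reached a given score on AV-101 is compared with a Group 4 subject who had that score without it. In item 5a the parent and LTE scores together amount to adjusting for the 24-week change in REVEAL. Parent-study improvement status, if added, is the same response at an earlier time.

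At stake are the reported odds ratios of Group 1 against Groups 4, 3 and 2 for first-tier endpoints. Leaving one covariate optional also leaves a modelling choice open after results are visible.

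**Working it through.** **No planned figure to reproduce.** The documents give no response rate, effect size or power for these models. Everything numerical below is illustrative and rests on assumed effects.

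**How far the covariate can move with the response.** From Table 3, WHO FC III to II changes the score by −1, NT-proBNP from 300–1099 to below 300 pg/mL by −2, and 6MWD from 165–319 m to 320–439 m by −1: −1 − 2 − 1 = −4 points.

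**Simulation A (200,000 per group, one LTE visit, no clustering).** Assumptions:
- Latent severity s is N(0, 1) at parent baseline. Each 24-week step adds N(0.05, SD 0.45) and subtracts the drug shift.
- WHO FC is s + N(0, SD 0.3), cut at −1.3, 0 and 1.7.
- REVEAL-like score = round(6 + 2(s + N(0, SD 0.5))).
- NT-proBNP = exp(6.3 + 0.9s + N(0, SD 0.3)).
- 6MWD = 380 − 70s + N(0, SD 25).
- Responses are scored from the Section 8.4 baseline.

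With a 0.5 SD shift at parent Week 24, mean REVEAL at LTE entry was 5.09 in Group 1 and 6.10 in Group 4. That gap of about 1 point is drug effect.

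In the tables, the first odds ratio adjusts for the pre-AV-101 score. The second adjusts as planned: LTE score alone for WHO FC, both scores for clinical improvement.

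*Group 1 versus 4* (shifts: Group 1 at parent Week 24; Group 1 at LTE Week 24; Group 4 at LTE Week 24)

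| Shifts | WHO FC | Clinical improvement |
|---|---|---|
| 0.3; 0.4; 0.3 | 0.79 → 0.77 | 1.50 → 1.34 |
| 0.5; 0.6; 0.5 | 0.70 → 0.66 | 1.32 → 1.12 |
| 0.5; 0.8; 0.5 | 1.16 → 1.10 | 1.98 → 1.68 |
| 0.7; 0.8; 0.7 | 0.62 → 0.56 | 1.22 → 0.98 |
| 0.5; 0.6; 0.35 | 1.04 → 0.99 | 1.96 → 1.63 |
| 0.5; 0.5; 0.5 | 0.55 → 0.52 | 1.09 → 0.91 |

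*Group 1 versus 2* (shifts: Group 1 at both times; Group 2 at both times). Share of log odds ratio lost = 1 − ln(planned) ÷ ln(pre-AV-101). First row, WHO FC: 1 − ln 1.29 ÷ ln 1.34 = 1 − 0.2546 ÷ 0.2927 = 13%.

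| Shifts | WHO FC | Lost | Clinical improvement | Lost |
|---|---|---|---|---|
| 0.3, 0.4; 0.1, 0.25 | 1.34 → 1.29 | 13% | 1.37 → 1.21 | 39% |
| 0.5, 0.6; 0.2, 0.45 | 1.39 → 1.30 | 20% | 1.37 → 1.14 | 58% |
| 0.7, 0.8; 0.3, 0.6 | 1.63 → 1.47 | 21% | 1.46 → 1.17 | 59% |
| 0.5, 0.5; 0, 0.2 | 1.89 → 1.72 | 15% | 1.88 → 1.37 | 50% |

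Every planned odds ratio is lower, and the larger losses are in the model with both scores.

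**Simulation B (is the direction robust?).** Only a REVEAL score is modelled: N(6.5, SD 2) at parent baseline, noise SD 1.3, a 1-point effect by Week 24, and half of it recovered by Group 4 at LTE Week 24. Response is no worsening from the Section 8.4 baseline. Group 1 versus 4 odds ratios, adjusted for parent / LTE / both:
- Noise that persists to later visits: 1.31 / 1.15 / 0.84.
- Purely visit-specific noise: 2.25 / 2.68 / 4.28.

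A variant with the same effect and catch-up gave 2.78 / 2.42 / 1.66 with persistent noise, 1.66 / 1.66 / 1.65 with mixed noise and 1.48 / 1.68 / 2.32 with visit-specific noise. So the adjustment can pull the odds ratio down, leave it alone or push it up.

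**Scoring from LTE entry instead.** In Simulation A the covariate then hardly mattered for Group 1 versus 4. In the second scenario, WHO FC was 0.34 with either score, and clinical improvement was 0.36 with the pre-AV-101 score against 0.35 with both. Under Simulation B's assumptions even this depended on how persistent the noise was.

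**The case against.** Four points have weight.

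- **The response baseline is unclear.** Item 3 speaks of visits after LTE baseline and of baseline WHO FC without saying which baseline, and item 2 next to it uses change from LTE baseline. If responses are scored from LTE entry, the LTE-entry score is an ordinary baseline covariate for a within-LTE question. This stands as an ambiguity. It does not remove the concern, because Section 8.4 sets the pre-AV-101 baseline for every efficacy analysis except delayed start.
- **Early start has its own test.** Section 8.5.1 compares Groups 1 and 4 on WHO FC improvement by a CMH test without REVEAL. That stands for WHO FC improvement in that one contrast. Section 8.5.1 names no clinical-improvement composite and does not cover Groups 2 and 3.
- **Low odds ratios are not all due to the covariate.** In Simulation A, four of the six Group 1 versus 4 WHO FC odds ratios are below 1 even with the pre-AV-101 score (0.79, 0.70, 0.62, 0.55). There Group 1 is scored over two 24-week steps and Group 4 over one. Changing the covariate will not cure that.
- **The stakes are limited.** The study objective is long-term safety, these effectiveness models carry no power claim, Section 8 defers detail to the SAP, and parent improvement status is optional. All true, and a reason to rank this below critical.

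A reader might infer that these models cannot show a benefit of earlier treatment, or that they must remove part of the drug effect. The documents do not support either. Both Group 1 and Group 4 receive the optimal dose in the LTE, so their contrast is early versus delayed start, and the direction of the distortion turns on assumptions the plan does not state.

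**Conclusion.** The concern holds as a defect of specification. In items 3 and 5a, with responses scored as Section 8.4 requires, the Group 1 versus 4, 3 and 2 odds ratios condition on a variable measured after treatment in Groups 1 and 2, and so do not estimate the effect of treatment history. That much follows from the text alone.

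The size does not. Under Simulation A the loss in Group 1 versus 2 is 13% to 21% of the log odds ratio for WHO FC and 39% to 59% for clinical improvement, and two of six Group 1 versus 4 clinical-improvement odds ratios cross from above to below 1. Simulation B shows the opposite direction when noise does not persist. The fair statement is that the planned adjustment may understate or even reverse a benefit of earlier treatment, that item 5a is potentially the worse case, and that neither size nor direction can be derived from the documents. It should be corrected before results are seen, but it does not threaten the study's main objective.

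**What to change.** In Section 8.5.2 items 3 and 5a and in the SAP:

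1. Replace LTE-entry REVEAL Lite 2 by the parent-trial baseline score for all groups. The alternative consistent with Section 8.4 is the score before first AV-101: parent baseline for Groups 1 and 2, LTE entry for Groups 3 and 4. In Simulation A the two choices gave Group 1 versus 4 odds ratios within 0.01 of each other.
2. Take parent-study improvement status out of the main item 5a model. Keep it, or the LTE-entry score, only in a labelled sensitivity analysis.
3. State that the responses in both items are scored from the Section 8.4 baseline. If a within-LTE question is wanted as well, define it as a separate analysis scored from LTE entry.

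The cost is wording. The parent score is already in item 5a and elsewhere in Section 8.5.2, and no new data are collected. The downside is possibly slightly lower precision, because the Week 24 score is likely more prognostic for LTE visits.

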3.1 Overall Design

Figure 1: Study Design of Study AV-101-003

For Subjects Entering the LTE from the Phase 2b and Intermediate Parts of AV-101-002

For Subjects Entering the LTE from the Phase 3 Part of AV-101-002

- A. Screening/Baseline Visit and procedures for the LTE will be conducted at the Week 24 Visit for AV-101-002.
- B. Once the optimal dose is selected for the parent Phase 3 Part of AV-101-002, subjects who enter the LTE from the Phase 2b Part and the Intermediate Part of AV-101-002 will be transitioned to the optimal dose.
- C. Once the AV-101 optimal dose has been selected, the LTE will no longer be blinded. Subjects enrolled during the Intermediate Part of AV-101-002 that enter the LTE study after the optimal dose is selected will be assigned to that dose upon completion of the Week 24 Visit for AV-101-002.

The doses administered in the Phase 2b and Intermediate parts of Study AV-101-002 are 10 mg, 35 mg, and 70 mg BID. In the LTE study subjects will continue on these doses and placebo subjects will be re-randomized to one of these active doses until such time as the optimal dose has been selected from the Phase 2b data based upon efficacy, safety, and tolerability. Once the optimal dose has been selected subjects in the LTE will be transitioned to the optimal dose. Subjects enrolled during the Intermediate Part of AV-101-002 that enter the LTE study after the optimal dose is selected will be assigned to that dose upon completion of the Week 24 Visit for AV-101-002. Subjects on the optimal dose or placebo in the Phase 3 Part of AV-101-002 will continue in the LTE at the optimal dose.

The schedule of activities and visit frequency will be similar to the parent study (AV-101-002) for the first 24 weeks of the LTE ([Table 1](#)). Thereafter, the interval between study visits will be increased to every 3 months. In the LTE study the quality-of-life instrument used will be the emPHasis-10 questionnaire. Investigators are encouraged to collect RHC hemodynamics in subjects who have in their opinion normalization or near normalization of hemodynamics on the transthoracic echo.

In a small cohort of subjects treated with oral imatinib for PAH, a responder analysis showed that the treatment duration for a complete hemodynamic response was approximately 3 years ([Speich, 2015](#)). Therefore, the LTE study will continue until 31 December 2025 or until the Sponsor stops the study.

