Visits within a subject form a cluster. Estimated proportions by treatment group and visit will be reported. For Week 24 after optimal dose treatment, the log of odds and proportions of subjects who maintain or improve WHO FC and their 95%CI will be reported by treatment groups. Odd ratios (OR) and 95%CI for subjects always on optimal dose (Group 1) relative to those subjects on always on placebo (Group 4) will be reported. OR and 95%CI among subjects always on optimal dose (Group 1) relative to those of subjects on placebo and then active treatment (Group 3) and OR and 95%CI among subjects always on optimal dose (Group 1) relative to those of subjects on non-optimal dose (Group 2) will also be reported.

4) Time to Clinical Worsening

Time to clinical worsening while in the parent trial and LTE will be based on the first occurrence of any of the following events for each subject.

- Death
- Initiation of parenteral prostanoids
- Hospitalization for worsening PAH
- $\geq 15\%$ decline from baseline in 6MWD and accompanied with progression to or continued WHO FC III or IV symptoms

A subject is evaluated for experiencing any of the above components of clinical worsening throughout the parent trial and LTE study period. Time to clinical worsening is the number of days between the earliest occurrence of the clinical worsening component and the date of the first dose in the parent trial. With treatment groups that change over time intervals, event and censoring will be defined within each time interval. A subject who does not experience any of the clinical worsening component throughout a treatment period/interval is censored and is assigned time to worsening status by the end of the interval. Subjects who are lost to follow-up are typically considered censored. Supplemental analyses will be performed where subjects with an unknown clinical worsening event will be considered to

experience the event and the time to clinical worsening status is the last contact with the subject.

The probability of clinical worsening every 24 weeks after the first dose in the parent trial throughout the LTE will be reported, descriptively as well as based on a Cox model for time to clinical worsening while holding covariates at their means.

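### Cox-based probabilities of clinical worsening taken at the covariate means are not average risks: too low below about 60% cumulative risk, too high above it

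*Combined protocol and SAP*

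**What the plan says.** Item 4 of Section 8.5.2 (Time to Clinical Worsening) states: "The probability of clinical worsening every 24 weeks after the first dose in the parent trial throughout the LTE will be reported". It gives two routes to that figure: a descriptive one, and one "based on a Cox model for time to clinical worsening while holding covariates at their means".

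The model is described next: "A Cox model will be fitted to time to clinical worsening with terms for time-varying by treatment dose groups". Its covariates are a "continuous LTE baseline REVEAL Lite 2.0 score (among those randomized to placebo in Phase 3") and a "continuous parent baseline REVEAL Lite 2.0 score, and IPAH/HPAH or Non-IPAH/HPAH category". The treatment comparison is the pairwise hazard ratio with a 95% CI for Group 1 against Groups 4, 3 and 2. The item ends: "Kaplan-Meier curves by parent trial treatment groups will be generated".

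The item does not call for averaging predictions over subjects. It does not say whether the means are taken overall or within groups, which treatment path is used for a time-varying treatment term, or how a mean is formed for a score that is listed for only some subjects.

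**The concern.** A reader will take a probability of worsening at 24, 48 or 72 weeks as the share of these patients expected to have worsened by then. A Cox curve at the covariate means does not estimate that share. Risk is a curved function of the linear predictor, so the risk at the average covariate differs from the average of the subjects' risks. The mean of a binary aetiology term also describes no one.

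The model-based and descriptive figures would therefore disagree even if the Cox model were exactly right. The plan gives no guidance on which to believe. The gap also changes sign along the curve, so the shape of the reported course over time is distorted as well as its level. Separately, two programmers following the same sentence could form the means differently and produce different tables.

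**Working it through.** **Inputs from the documents.** The quantity, the method and the covariates are those of Section 8.5.2, item 4. No worsening rate, REVEAL Lite 2.0 distribution, Cox coefficient or event count is given, so there is no planned figure to reproduce.

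**Assumptions.** Score: rounded normal, mean 6, limited to 1–14, SD 1.5 to 2.5. Hazard ratio (HR): 1.2 to 1.5 per point. The main table uses the score alone.

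**Formulas.** Let H be the cumulative hazard at the mean score m.

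- Reported figure: 1 − exp(−H).
- Average risk: the mean over subjects of 1 − exp(−H × HR^(x − m)).

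**Direction.** Write LP for the centred linear predictor and u = H × exp(LP). The second derivative of risk in LP is u × exp(−u) × (1 − u). Risk is convex where u is below 1 and concave where it is above 1. So the figure at the means is too low at small cumulative hazard and too high at large. With very small spread the change comes at 1 − exp(−1) = 63%. Over spreads of LP from SD 0.25 to 1.25 it lies between 57% and 63%.

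**Size.** For each scenario, H was solved so that the average risk equals the stated true value; the table shows 1 − exp(−H).

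| Score SD | HR per point | SD of LP = SD × ln(HR) | True 20% | True 40% | True 80% |
|---|---|---|---|---|---|
| 1.5 | 1.2 | 1.5 × 0.182 = 0.27 | 19.5% | 39.4% | 80.8% |
| 2.0 | 1.3 | 2.0 × 0.262 = 0.52 | 18.2% | 38.2% | 82.7% |
| 2.5 | 1.5 | 2.5 × 0.405 = 1.01 | 14.6% | 34.9% | 88.8% |

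At a true 20% the shortfall runs from 20 − 19.5 = 0.5 to 20 − 14.6 = 5.4 points. At a true 80% the excess runs from 0.8 to 8.8 points. Adding a binary aetiology term (assumed HR 0.7, prevalence 60%) leaves the crossover at 58% to 62%.

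**Check with a fitted model.** In a simulation of 20,000 subjects (SD of LP 0.75), a Cox model was fitted and its baseline hazard estimated:

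| At the means | Averaged over subjects | Observed |
|---|---|---|
| 10.4% | 12.8% | 12.8% |
| 21.8% | 25.4% | 25.4% |
| 52.8% | 54.1% | 54.0% |
| 63.2% | 62.5% | 62.5% |
| 70.8% | 68.6% | 68.5% |
| 85.9% | 80.7% | 80.6% |

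The averaged prediction follows the observed risk throughout. The prediction at the means crosses it.

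**Where this trial would lie.** Section 1.1 cites registry survival of 85%, 68%, 57% and 49% at 1, 3, 5 and 7 years, so deaths of 15%, 32%, 43% and 51%. Used only as illustrative risk levels, these would be reported as about 12%, 28%, 40% and 49% (SD of LP 0.75). The composite adds three further kinds of event, and "the LTE study will continue until 31 December 2025 or until the Sponsor stops the study", with no stated follow-up per subject. Early marks probably fall below the crossover; later marks cannot be placed.

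**Forming the means.** The parent-baseline score can be averaged over everyone. The LTE-baseline score is listed only for subjects randomized to placebo in Phase 3, so neither its mean nor its individual value is defined for the rest.

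**The case against.** The strongest reply is that the figure at the means is an openly labelled conditional estimate, reported beside a descriptive probability and Kaplan-Meier curves, while the treatment comparison rests on hazard ratios that this choice does not touch. That largely stands. A reader might infer that the headline result is biased, but the documents give this figure no such rank, and the stated objective is long-term safety and tolerability. The descriptive results do not make the model figure right, though, and the Kaplan-Meier curves are by parent-trial arm rather than by LTE Groups 1 to 4.

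A reader might also infer that the reported risks will always be too favourable. That holds only below the crossover, and the documents give no worsening rate that would keep every 24-week mark there.

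A third tempting inference is that the error fails to cancel between LTE groups with different score spread. That presumes reporting by LTE group with group-specific means, and item 4 states neither. With one common set of means, the model curves differ only through treatment.

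The size may also be small. At a score SD of 1.5 to 2.0 and HR 1.2, the gap is about 1 point or less at true risks of 20% to 40%. For comparison, with all 370 expected subjects and no censoring, the 95% half-width is 1.96 × √(0.2 × 0.8 / 370) = 4.1 points at 20% and 1.96 × √(0.4 × 0.6 / 370) = 5.0 points at 40%. This tempers the point, but sampling error is shown by an interval and this discrepancy is not.

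Finally, Section 8 defers detail to a SAP. Holding covariates at their means is, however, a method already chosen and not a gap left to be filled.

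**Conclusion.** The point holds as a cheap improvement to a stated method for a first-tier endpoint. It does not threaten the treatment comparison. The planned model-based probabilities describe a hypothetical average subject. They fall short of the average risk below about 60% cumulative risk and exceed it above.

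The change of sign follows from the form of the model. The sizes rest on the assumed score spread and hazard ratio: from half a point to about 5 points too low at true risks of 20% to 40%, and about 1 to 9 points too high at 80%. The missing definition of the mean for the LTE-baseline score needs no assumption: it can be read directly from item 4.

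**What to change.** In Section 8.5.2, item 4, and in the SAP, replace prediction at the covariate means with direct standardisation:

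- Name one common analysis population and each treatment path for which a curve is wanted, since the treatment term is time-varying.
- Under each path, predict the curve for every subject in that population from the subject's own baseline covariates.
- Average the curves, read the average every 24 weeks, and give bootstrap 95% CIs.
- In this prediction model use the parent-baseline REVEAL Lite 2.0 score, which is defined for all subjects, or state how the LTE-baseline score enters for those not randomized to placebo in Phase 3.

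Using one population under every path keeps case-mix differences between groups out of the comparison of curves.

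The cost is a few sentences of text, modest extra programming and bootstrap run time. The treatment paths must be written down in advance. No data collection or trial conduct changes.
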